## Protocol for non-interventional studies based on existing data

Document Number:	c30445781-01
BI Study Number:	1237-0090
BI Investigational Product(s):	Stiolto® Respimat®
Title:	The Role of Inhaler Device in the Treatment Persistence with Dual Bronchodilators in Patients with COPD
Protocol version identifier:	1.0
Date of last version of protocol:	N/A
PASS:	No
EU PAS register number:	Study not registered
Active substance:	Olodaterol and Tiotropium Bromide (ATC R03AL06) Umeclidinium and Vilanterol (ATC R03AL03)
Medicinal product:	Stiolto® Respimat®; Anoro® Ellipta®
Product reference:	N/A
Procedure number:	N/A
Joint PASS:	No
Research question and objectives:	
The primary objective of the study is to use US data to determine relative persistence between Olodaterol/Tiotropium Bromide delivered with the Respimat soft mist inhaler and Umeclidinium/Vilanterol delivered with the Ellipta dry powder inhaler using a 1:2 propensity score matched analysis.
 
The secondary objectives of the study are as follows:
 
 
- Characterize new users of Olodaterol/Tiotropium Bromide and Umeclidinium/Vilanterol in terms of demographics, medication use, comorbidities, and other variables, before and after propensity score matching.
 
- Determine the incidence rate and proportion of patients discontinuing or switching among new users of Olodaterol/Tiotropium Bromide and Umeclidinium/Vilanterol.
 
- Determine the relative rate and proportion of patients discontinuing between Olodaterol/ Tiotropium Bromide and
 

	Umeclidinium/Vilanterol. using a standard multivariate analysis (If feasible).
Country(-ies) of study:	United States
	T: Email:
Author:	T: Email:
	BI contact person:
Marketing authorisation holder(s):	
MAH contact person:	
In case of PASS, add:	N/A
In case of PASS, add:	N/A
Date:	22 November 2019
Page 1 of 69	
Proprietary confidential information © 2019 Boehringer Ingelheim International GmbH or one or more of its affiliated companies. All rights reserved. This document may not - in full or in part - be passed on, reproduced, published or otherwise used without prior written permission	

## **2. LIST OF ABBREVIATIONS**

ACE	Angiotensin Converting Enzyme
AIDS	Acquired Immune Deficiency Syndrome
CCAE	Commercial Claims and Encounters
CDCI	Charlson Deyo Comorbidity Index
CI	Confidence Interval
COB	Coordination of Benefits
COBRA	Consolidated Omnibus Budget Reconciliation Act
COPD	Chronic Obstructive Pulmonary Disease
CT	Computed Tomography
DPI	Dry Powder Inhaler
ENCEPP	European Network of Centres for Pharmacoepidemiology and Pharmacovigilance
ESRD	End Stage Renal Disease
FDC	Fixed Dose Combination
GLP-1	Glucagon-like Peptide-1
GOLD	Global Initiative for Chronic Obstructive Lung Disease
HIV	Human Immunodeficiency Virus
ICD	International Classification of Diseases
ICS	Inhaled Corticosteroid
IP	Inpatient
IQR	Interquartile Range
IRB	Institutional Review Board
LABA	Long-Acting Beta-Agonists
LAMA	Long-Acting Muscarinic Antagonists
NDC	National Drug Code
NSAID	Nonsteroidal Anti-inflammatory Drug
OCS	Oral Corticosteroid
OP	Outpatient
SABA	Short-acting Beta Agonist
SAMA	Short-acting Muscarinic Antagonist
SD	Standard Deviation
SMI	Soft Mist Inhaler

## 4. ABSTRACT

Name of company: Boehringer Ingelheim International GmbH			
Name of finished medicinal product: Stiolto® Respimat®; Anoro® Ellipta®			
Name of active ingredient: Olodaterol and Tiotropium Bromide (ATC R03AL06); Umeclidinium and Vilanterol (ATC R03AL03)			
Protocol date: 22 November 2019	Study number: 1237-0090	Version/Revision: 1.0	Version/Revision date: NA
Title of study:	The Role of Inhalers In Treatment Persistence With Dual Bronchodilators In Patients With COPD		
Rationale and background	
Inhaled therapies are the cornerstone of chronic obstructive lung disease (COPD) management approaches. The aim of inhaled therapy is to deliver therapeutic agents directly to the lungs, optimizing benefits while minimizing the potential for treatment-related adverse effects (Braido 2016).
 
Adherence to COPD therapies involves patients initiating their prescribed therapy, implementing it as prescribed (i.e., correctly administering the prescribed dose at the physician directed frequency), and persisting with treatment (Braido 2016; Mäkelä 2013). Also central to the therapeutic benefit of inhaled therapies is their successful administration, which requires patients to have knowledge and understanding of (and ability to implement) the appropriate inhaler technique required to optimize both the dispensed and administered doses (Braido 2016). Inspiratory capabilities of patients with COPD are affected by increasing static and dynamic hyperinflation and weakening of the respiratory muscles, causing many patients to have peak inspiratory flow rates that are suboptimal to use many dry-powder inhalers (DPIs) (Sohini 2017). This paradoxical situation may lead to improper inhalation that prevents successful drug delivery to the lungs, which may affect treatment efficacy. The question if different devices, DPI and Soft Mist Inhalers (SMI), played a role in treatment persistence remains to be answered.
 
In this study we aim to compare the persistence in using two different medications from the same drug class (LAMA/LABA FDC) which are delivered through different devices, a DPI and an SMI.
		

Name of company: Boehringer Ingelheim International GmbH			
Name of finished medicinal product: Stiolto® Respimat®; Anoro® Ellipta®			
Name of active ingredient: Olodaterol and Tiotropium Bromide (ATC R03AL06); Umeclidinium and Vilanterol (ATC R03AL03)			
Protocol date: 22 November 2019	Study number: 1237-0090	Version/Revision: 1.0	Version/Revision date: NA
Research question and objectives:	
This study seeks to compare the differences in treatment persistence in using two combinations of two drugs of the same drug class (LAMA/LABA as a fixed dose combination) delivered through different devices (a DPI or an SMI) within an administrative claims database in the US.
 
The primary objective of the study is to use US data to determine relative treatment persistence between patients prescribed Olodaterol/Tiotropium Bromide delivered with the Respimat SMI and Umeclidinium/Vilanterol delivered with the Ellipta DPI using a 1:2 propensity score matched analysis.
 
The secondary objectives of the study are as follows:
 
 
- Characterize new users of Olodaterol/Tiotropium Bromide and Umeclidinium/Vilanterol in terms of demographics, medication use, comorbidities, and other variables, before and after propensity score matching.
 
- Determine the rate and risk (proportion of patients) of discontinuation among new users of Olodaterol/Tiotropium Bromide and Umeclidinium/ Vilanterol in the 1:2 matched cohort.
 
- Determine the relative rate and risk of discontinuation between Olodaterol/Tiotropium Bromide and Umeclidinium/Vilanterol, using a standard multivariable analysis (Same variables as propensity score model) in the total unmatched cohort.
 
		
Study design:	
New-user cohort design with propensity scores used to match up to 2 Umeclidinium/Vilanterol initiators to each Olodaterol/Tiotropium Bromide initiator.
		
Population:	
Patients initiating Olodaterol/Tiotropium Bromide or Umeclidinium/Vilanterol between 17 November 2015 and 31 March 2018.
 
Exclusion criteria are:
 
 
• Aged <40 years.
 
• Enrolment with medical and pharmacy coverage prior to the cohort entry < 180 days.
 
• Never had COPD diagnosis on the cohort entry date or prior to cohort entry.
 
		

Name of company: Boehringer Ingelheim International GmbH			
Name of finished medicinal product: Stiolto® Respimat®; Anoro® Ellipta®			
Name of active ingredient: Olodaterol and Tiotropium Bromide (ATC R03AL06); Umeclidinium and Vilanterol (ATC R03AL03)			
Protocol date: 22 November 2019	Study number: 1237-0090	Version/Revision: 1.0	Version/Revision date: NA
		

• A record for dispensed Olodaterol/Tiotropium Bromide delivered with Respimat inhalator or Umeclidinium/Vilanterol delivered with the Ellipta Inhaler during the 180-day baseline prior to cohort entry.

• Diagnosis of asthma any time prior to cohort entry.

• Diagnosis of lung cancer any time prior to cohort entry.

• Diagnosis of lung transplant any time prior to cohort entry.

	

Name of company: Boehringer Ingelheim International GmbH			
Name of finished medicinal product: Stiolto® Respimat®; Anoro® Ellipta®			
Name of active ingredient: Olodaterol and Tiotropium Bromide (ATC R03AL06); Umeclidinium and Vilanterol (ATC R03AL03)			
Protocol date: 22 November 2019	Study number: 1237-0090	Version/Revision: 1.0	Version/Revision date: NA

Variables:
 
Exposures
 
 
• Olodaterol/Tiotropium Bromide (Stiolto®) delivered via Respimat inhaler
 
• Umeclidinium/Vilanterol (Anoro®) delivered via Ellipta Inhaler
 
 
Outcome
 
 
• Discontinuation of index treatment (Olodaterol/Tiotropium Bromide or Umeclidinium/Vilanterol), defined as persistence of treatment (no refill claim within 60 days (allowable grace period) after end of <n> days supply). Addition of another drug will not count as a discontinuation.
 
 
Covariates
 
Demographics
 
 
• Age on the cohort entry date
 
• Sex (Male, Female)
 
• Region (Northeast, North Central, South, West, Unknown, Missing)
 
• Insurance Type (Commercial, Medicare, Missing)
 
• Study Year of Cohort Entry (First Year: 17 Nov 2015-30 Nov 2016, Second Year: 01 Dec 2016-30 Nov 2017, Third Year: 01 Dec 2017-31 Mar 2018)
 
 
Concomitant Medications
 
 
• Oral Corticosteroids (OCS)
 
• Short acting muscarinic antagonist (SAMA)
 
• Short acting beta agonist (SABA)
 
• Long acting muscarinic antagonist (LAMA)
 
• Long acting beta agonist (LABA)
 
• Inhaled corticosteroid (ICS)
 
• LAMA / LABA combination (that is not Stiolto or Anoro)
 
• LABA / ICS combination
 
• LAMA / LABA / ICS combination
 
• NSAIDs
 
• Antihistamines
 
			

Name of company: Boehringer Ingelheim International GmbH			
Name of finished medicinal product: Stiolt® Respimat®; Anoro® Ellipta®			
Name of active ingredient: Olodaterol and Tiotropium Bromide (ATC R03AL06); Umeclidinium and Vilanterol (ATC R03AL03)			
Protocol date: 22 November 2019	Study number: 1237-0090	Version/Revision: 1.0	Version/Revision date: NA

 
● Opioids
 
● Oral antibiotics
 
● Antidiabetic Agents (not including insulin)
 
● Insulin (basal or mealtime)
 
● Methotrexate
 
● Statins
 
● Antihypertensives
 
● Anticoagulants
 
● Anti-psychotic/anti-depressives/anxiolytic
 
● Oxygen therapy
 
 
Comorbidities/Symptoms
 
 
● History of All-Cause Hospitalization
 
● History of Emergency Department Visit
 
● History of Hospitalization due to Respiratory Condition
 
● Acute Myocardial Infarction
 
● Angina Pectoris
 
● Peripheral Vascular Disease
 
● Heart Failure
 
● Hypertension
 
● Upper Respiratory Infection
 
● Lower Respiratory Infection
 
● Cardiac Arrhythmias
 
● Cerebrovascular Disease
 
● All cancers (except non-melanoma skin cancer)
 
● Allergic Rhinitis
 
● Chronic Sinusitis
 
● Bronchiectasis
 
● Pneumonia
 
● Chronic Bronchitis
 
● Exertional Breathlessness
 
● Anxiety
 
● Dementia
 
● Depression
 
● Osteoporosis
 
● Charlson-Deyo Comorbidity Index
 
			

Name of company: Boehringer Ingelheim International GmbH			
Name of finished medicinal product: Stiolto® Respimat®; Anoro® Ellipta®			
Name of active ingredient: Oladaterol and Tiotropium Bromide (ATC R03AL06); Umeclidinium and Vilanterol (ATC R03AL03)			
Protocol date: 22 November 2019	Study number: 1237-0090	Version/Revision: 1.0	Version/Revision date: NA

 
● Acute Liver Injury or Failure
 
● Chronic Kidney Disease (without ESRD)
 
● End Stage Renal Disease
 
● Rheumatic Disease
 
● Peptic Ulcer Disease
 
● Gastroesophageal Reflux Disease
 
● Type 1 Diabetes Mellitus
 
● Type 2 Diabetes Mellitus
 
● HIV/AIDS
 
● Hemiplegia or Paraplegia
 
 
Lifestyle
 
 
● Smoking-related claim
 
● Vaccination for Influenza
 
● Vaccination for Pneumococcus
 
 
Respiratory Function Procedures/Tests Conducted
 
 
● Pulmonary function tests
 
● Six-minute walk test
 
● Chest X-ray
 
● High resolution chest CT
 
			

Name of company: Boehringer Ingelheim International GmbH			
Name of finished medicinal product: Stiolto® Respimat®; Anoro® Ellipta®			
Name of active ingredient: Olodaterol and Tiotropium Bromide (ATC R03AL06); Umeclidinium and Vilanterol (ATC R03AL03)			
Protocol date: 22 November 2019	Study number: 1237-0090	Version/Revision: 1.0	Version/Revision date: NA
Data sources:	Truven MarketScan is a claims database that captures longitudinal, individual-level administrative claims data from the United States.		
Study size:	There are 14,751 new users of Olodaterol/Tiotropium Bromide or Umeclidinium/Vilanterol between 17 November 2015 and 31 March 2018 who satisfied the inclusion criteria. Among them, 3,889 initiated Olodaterol/Tiotropium Bromide and 10,862 initiated Umeclidinium/Vilanterol).		
Data analysis:	
For demographic and lifestyle variables, the value recorded on the cohort entry date will be reported, otherwise the most recent known value will be reported. Presence of comorbidities and use of concomitant medication use will be determined based whether they ever occurred within the 180-day baseline period preceding the index date. Differences in the confounder distributions will be inspected for successful confounder balance of measured characteristics.
 
Patients will be followed up until first occurrence of death, discontinuation, disenrollment, end of data, or 365 days.
 
The data will be displayed in a nonparametric fashion on a persistency curve (a Kaplan–Meier curve) with discontinuation considered as elimination.
 
Unmatched Cohort Rates and risks (proportion of patients) with the outcomes for each exposure group will be reported among the unmatched cohort.
 
Matched Cohort Rates and risks (proportion of patients) with the outcomes for each exposure group will be reported among the matched cohort.
 
Logistic regression will be used to calculate the propensity to initiate Olodaterol/Tiotropium Bromide versus Umeclidinium/Vilanterol. The propensity score will then be used to identify up to 2 initiators of Umeclidinium/Vilanterol for each initiator of Olodaterol/Tiotropium Bromide with the same propensity score (<math>\pm</math> a caliper of 5%) as the corresponding initiator of Olodaterol/Tiotropium Bromide.
		

Name of company: Boehringer Ingelheim International GmbH			
Name of finished medicinal product: Stiolto® Respimat®; Anoro® Ellipta®			
Name of active ingredient: Olodaterol and Tiotropium Bromide (ATC R03AL06); Umeclidinium and Vilanterol (ATC R03AL03)			
Protocol date: 22 November 2019	Study number: 1237-0090	Version/Revision: 1.0	Version/Revision date: NA

Cox proportional hazard regression model will be used to assess the relative rate (or hazard) of the outcome in patients treated with Olodaterol/Tiotropium Bromide compared to patients treated with Umeclidinium/Vilanterol during the one-year follow-up. Crude HRs and 95% CIs will be reported for the matched cohorts.
 
Among the matched cohort, relative risks with 95% CIs will also be reported, as assessed by conditional logistic regression.
 
Relative rates and risks will also be reported using standard multivariable regression.
 
Sensitivity Analyses
 
 
• Restrict the 60-day allowable grace period used to define the discontinuation outcome to 30 days.
 
• Increase the 60-day allowable grace period used to define the discontinuation outcome to 90 days.
 
• Start the patient identification period on 21 May 2015 immediately upon FDA approval.
 
• Exclude patients with ACOS. Patients with asthma only but not COPD are still excluded from cohort.
 
			
Milestones:	
 
- Feasibility assessment Sept 2018 (done)
 
- Draft study protocol Dec 2018
 
- Final study protocol Apr 2019
 
- Results tables available May 2019
 
- 1st Abstract submitted (ERS 2019, ISPOR or AMCP ) Jun 2019
 
- Manuscript submitted Q2 2019
 
		

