### Matched Cohort

A matched propensity score analysis will be used to assess comparative persistence between the two exposure comparison groups. Logistic regression will be used to calculate the propensity to initiate Olodaterol/Tiotropium Bromide versus Umeclidinium/Vilanterol given all covariates (except components of the Charlson Comorbidity index) listed in [section 9.3.3](#), according to the following model:

$$\text{Logit}(\text{Treatment} | X_1, X_2, \dots, X_n) = \beta_0 + \beta_1 * X_1 + \beta_2 * X_2 + \dots + \beta_n * X_n$$

Any covariates which are collinear with each other will be dropped from the analysis (if it causes failure of model to converge). The propensity score will then be used to identify up to 2 initiators of Umeclidinium/Vilanterol for each initiator of Olodaterol/Tiotropium Bromide with the same propensity score ( $\pm$  a caliper of 5%) as the corresponding initiator of Olodaterol/Tiotropium Bromide (Austin 2011).

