#### **9.3.3 Covariates**

Covariates will be identified based on data recorded within 180 days prior to or on the index date (date of dispensing/initiation of the exposure), unless otherwise specified. If multiple measurements are made in the baseline period, then the most recent measurement will be used.

Covariates will be used to predict propensity scores in later analyses. Absolute and relative frequencies of each covariate will also be reported in Table Shells 1 and 2 (see [Annex 5](#)). Detailed descriptions of the listed covariates can be found in [Annex 3](#) and [4](#).

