## Drug Duration

Unless otherwise noted, drug event duration was calculated from the “Day’s Supply” field, and in cases where this field was 0, the duration was assumed to be 1 day.

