#### 9.7.1.3 Comparative Persistence

- Relative Rate of Discontinuation of Olodaterol/Tiotropium Bromide vs Umeclidinium/Vilanterol in the Unmatched Cohort

Multivariable Cox proportional hazards models with all variables (except components of the Charlson Comorbidity index) in [section 9.3.3.](#) will be used to estimate the hazard ratios (HRs) and 95% CIs for Olodaterol/Tiotropium Bromide compared to patients treated with Umeclidinium/Vilanterol during follow-up for incident discontinuations, according to the following model:

$$h(t | \text{Treatment}, X_1, \dots, X_n) = h(t_0) * \exp(\beta_1 * \text{Treatment} + \beta_2 * X_2 + \dots + \beta_n * X_{n+1})$$

Where treatment can be 1=Stiolto or 0=Anoro and t = time to discontinuation

- Relative Risk of Discontinuation of Olodaterol/Tiotropium Bromide vs Umeclidinium/Vilanterol in the Unmatched Cohort

Multivariable logistic regression will be used to assess relative risk of discontinuation and 95% CIs for Olodaterol/Tiotropium Bromide compared to patients treated with Umeclidinium/Vilanterol during follow-up for incident discontinuations, according to the following model using all covariates (except components of the Charlson Comorbidity index) in [section 9.3.3.](#):

$$\text{Logit}(\text{Discontinuation}=1 | \text{Treatment}, X_1, X_2, \dots, X_n) = \beta_0 + \beta_1 * \text{Treatment} + \beta_2 * X_2 + \dots + \beta_n * X_{n+1}$$

- Relative Rate of Discontinuation of Olodaterol/Tiotropium Bromide vs Umeclidinium/Vilanterol in the Matched Cohort

Cox proportional hazards models with treatment as the only independent variable will be used to estimate the hazard ratios (HRs) and 95% CIs for Olodaterol/Tiotropium Bromide

compared to patients treated with Umeclidinium/Vilanterol during follow-up for incident discontinuations, according to the following model:

$$h(t | \text{Treatment}, X) = h_0(t) * \exp(\beta_1 * \text{Treatment})$$

Where treatment can be 1=Stiolto or 0=Anoro and t = time to discontinuation

- Relative Risk of Discontinuation of Olodaterol/Tiotropium Bromide vs Umeclidinium/Vilanterol in the Matched Cohort

Logistic regression will be used to assess relative risk of discontinuation and 95% CIs for Olodaterol/Tiotropium Bromide compared to patients treated with Umeclidinium/Vilanterol during follow-up for incident discontinuations, according to the following model:

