### 9.7.2 Sensitivity Analysis

Four sensitivity analyses will be conducted. For these analyses, in the interest of reducing the number of additional tables, only the descriptive statistics for the matched population ([Annex Table 2](#)), and primary results ([Annex Tables 4](#) and [5](#)) will be reported.

Two sensitivity analyses will be conducted to evaluate the robustness of the outcome definition:

1. Use of a 30-day Grace Period

Restrict the 60-day allowable grace period used to define the discontinuation outcome to 30 days to allow a gap of one month. This sensitivity analysis may be useful if the 60-day grace period is too lenient, as the usual day's supply of Stiolto is 30 days.

2. Use of a 90-day Grace Period

Since neither the Olodaterol/Tiotropium Bromide or Umeclidinium/Vilanterol drug products are available as generic formulations, the relatively high price of these medications may lead some patients to space out their doses to greater than the recommended dosing schedule or use one puff instead of two to prolong their medication supply. Patients may also neglect to take their medications due to forgetfulness or because they become less symptomatic. Thus, we will also increase the 60-day allowable grace period used to define the discontinuation outcome, to 90 days.

Two sensitivity analyses will be conducted in an attempt to increase the sample size:

3. Start Patient Identification Period in 21 May 2015

The primary identification period starts 180 days after Stiolto Respimat was approved by FDA for use in the US (21 May 2015) on 17 November 2015. This sensitivity cohort will start the patient identification period immediately upon FDA approval on 21 May 2015.

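### The index fill's days' supply shifts the earliest possible discontinuation date, but no propensity score, outcome model, balance table or sensitivity analysis accounts for it

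*Combined protocol and SAP*

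**What the plan says.** The Abstract (Outcome) defines discontinuation as "no refill claim within 60 days (allowable grace period) after end of" the days' supply; 9.3.2.1 repeats this. Section 9.6 (Drug Duration) states that "drug event duration was calculated from the" days' supply field of the claim, and that "in cases where this field was 0, the duration was assumed to be 1 day". On follow-up the Abstract says: "Patients will be followed up until first occurrence of death, discontinuation, disenrollment, end of data, or 365 days".

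Section 9.3.3 says "Covariates will be used to predict propensity scores in later analyses". The propensity model in 9.2.2 (Matched Cohort) is fitted "given all covariates (except components of the Charlson Comorbidity index) listed in" that section. The unmatched analysis in 9.7.1.3 uses "Multivariable Cox proportional hazards models with all variables (except components of the Charlson Comorbidity index) in" the same section, and the multivariable logistic model takes the same list. The matched Cox model contains treatment alone.

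The list covers demographics, medications, comorbidities, lifestyle and respiratory tests. It has no days' supply, quantity or dispensing-channel item, and Table shells 2 and 3 have no such row. The only fill size given anywhere is in 9.7.2: the usual "supply of Stiolto is 30 days". Nothing is said for Anoro.

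**The concern.** The comparative question is relative persistence, and part of the outcome clock is set at dispensing, before the patient has done anything. Two patients who stop on the same day have different event dates if one was given 30 days and the other 90. If one product has more long fills than the other after matching, it will look more persistent even when patients stop at the same rate.

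Matching on the listed covariates would remove this only so far as those covariates stand in for fill size, and no planned table would show whether they had. The grace-period analyses could also be misread as reassurance. They move both fill sizes by the same amount, so agreement across them says nothing about a difference in fill mix.

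**Working it through.** **Plan's own figure.** Section 9.5 gives 3,889 Tio/Olo and 10,862 Umec/Vi initiators: 3,889 + 10,862 = 14,751, as stated. Full 1:2 matching needs 2 × 3,889 = 7,778 comparators, which are available. No power or event calculation is given.

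**Earliest event day.** Index days' supply, plus the grace period if the event is dated at its end. The 90-day fill is an assumption; the documents mention only 30 days.

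| Dating rule | 30-day fill | 90-day fill | Gap |
|---|---|---|---|
| End of 60-day grace (primary) | 30 + 60 = 90 | 90 + 60 = 150 | 60 |
| End of 30-day grace | 60 | 120 | 60 |
| End of 90-day grace | 120 | 180 | 60 |
| End of supply | 30 | 90 | 60 |

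A claim with zero days' supply, reset to 1, gives 1 + 60 = day 61. The gap is 60 days under every rule.

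**Illustration with identical stopping in both arms.** Assumptions, none from the documents:
- 25% stop after the first 30 days, then 8% per further 30 days.
- Supply runs to the end of the current fill, and fill size is constant within patient.
- Follow-up is 365 days with no other censoring.
- 10% of Tio/Olo patients have 90-day fills; the Umec/Vi share is varied.

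Apparent hazard ratio, Tio/Olo against Umec/Vi, from a treatment-only Cox model:

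| Setting | 10% v 10% | 10% v 20% | 10% v 30% |
|---|---|---|---|
| 60-day grace, end-of-grace dating | 1.00 | 1.02 | 1.04 |
| Same, stratified by index fill size | 1.00 | 1.00 | 1.00 |
| End-of-supply dating | 1.00 | 1.01 | 1.03 |
| 30-day grace | 1.00 | 1.02 | 1.05 |
| 90-day grace | 1.00 | 1.01 | 1.03 |

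Reversing which arm has more long fills reverses the direction.

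**Set against precision.** This model gives about 64% events: 0.64 × 3,889 = 2,489 and 0.64 × 7,778 = 4,978, so SE(log HR) = √(1/2,489 + 1/4,978) = 0.025. At 52% events, √(1/2,010 + 1/4,020) = 0.027. Under the 60-day grace period and either dating rule, the log hazard ratios for 10 to 20 point imbalances run from 0.013 to 0.038 before rounding. 0.013/0.025 = 0.5 and 0.038/0.025 = 1.5 standard errors. A bias of b standard errors makes a nominal 95% interval exclude 1 with probability P(|Z + b| > 1.96): about 8% at b = 0.5 and 32% at b = 1.5, instead of 5%.

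**Other stopping assumptions.** With exponential stopping (medians 120, 180 and 365 days), end-of-grace dating gave 1.01 to 1.03 for 10% v 20% and 1.03 to 1.05 for 10% v 30%. End-of-supply dating gave 1.00 to 1.02 and 1.01 to 1.05. Simulation error was about 0.005 to 0.007 on the log scale, so differences of 0.01 in this set should not be read closely.

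**The case against.** The strongest reply is that the harm depends on facts the documents do not contain. They mention no 90-day fills, no mail order and no difference in fill mix between products. Insurance type, region, age and year of entry are matched and may act as partial proxies for fill size. This stands: size and direction cannot be determined from the plan. It does not remove the omission, because no planned output would show whether the mix is balanced.

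A reader might infer that days 90 and 150 are fixed by the protocol. They are not, since no event-dating rule is given; only the 60-day gap is firm. A reader might also infer that the plan overlooks the difference between supply and use. It does not: 9.9 and 9.12 both say that a filled claim does not show consumption, and 9.12 notes the resulting overestimate of persistence. What is missing is the possible difference between arms.

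It can also be argued that index days' supply belongs to the exposure dispensing, so it is not clearly a pre-treatment confounder for a product-choice model, and that it covers only the first fill. Both points have force. They are reasons to pair the covariate with a restricted or stratified analysis, and to state that changes in fill size after index stay unadjusted.

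**Conclusion.** The concern holds in a conditional form. By the outcome definition, index-fill days' supply shifts the earliest possible event, by 60 days between a 30- and a 90-day fill, and nothing in the analysis plan accounts for it. The bias is zero if fill mix is equal after matching. For assumed 10 to 20 point imbalances it is about 1.01 to 1.04 on the hazard ratio under a true null, roughly 0.5 to 1.5 standard errors; other stopping assumptions widen this to about 1.00 to 1.05.

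The documents do not support the stronger inference that the planned hazard ratio is biased, or that it favours one product, because they give no fill shares for either arm. Nor do they support a claim that the change would need an exception to the covariate window: 9.3.3 already admits data recorded on the index date. This is a worthwhile, inexpensive improvement to the primary comparison and not a demonstrated error in it.

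**What to change.** - Add days' supply of the index fill (30 or fewer, 31–89, 90 or more) to 9.3.3, so that it enters the propensity score and both multivariable models.
- Add the same row to Tables 2 and 3. If the arms are balanced, the row will show it.
- Add a sensitivity analysis restricted to index fills of 30 days or fewer, or stratified by index fill size.
- State in 9.3.2.1 whether the event is dated at the end of supply or the end of grace.
- Bring the baseline wording in 9.2.1 and 9.7.1.1, which ends before the index date, into line with 9.3.3, which includes it.

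The cost is one covariate from a field already used to build the outcome, and one further analysis; no new data are needed. There are two downsides. Some matches may be lost if fill mix differs strongly by product, which is also the case where adjustment matters most. Changes in fill size after the index claim remain unadjusted and should be listed as a limitation in 9.9.
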